### **6.2.3 Efficacy Assessments**

The following assessments will be considered as efficacy measurements.

- Urine volume, urinary creatinine, and the average of two serum creatinine measurements will be used for the calculation of time-corrected endogenous creatinine clearance at all visits from baseline to Day 7, and will be calculated by the central laboratory. The measurements from Day 1 to Day 7, inclusive, will be used to calculate the primary endpoint. Only if reliable urine collection is possible, urine will be collected on Days 14, 21, and 28 for time-corrected endogenous creatinine clearance calculation (i.e., patient is in the ICU or intermediate care unit or hospital). If reliable urine collection is not possible, one serum creatinine sample still needs to be taken for calculating eGFR.

- Urine volume collection in a  $6 \pm 1$  hour collection period at baseline and at all visits from Day 1 to Day 28, but only required if reliable urine collection is possible (i.e., patient is in the ICU or intermediate care unit or hospital)
- BUN clearance at all visits from Day 1 to Day 7.
- Urinary urea at baseline and at all visits from Day 1 to Day 28, only if reliable urine collection is possible (i.e., patient is in the ICU or intermediate care unit or hospital)
- Fractional excretion of sodium at all visits from baseline to Day 7
- Fractional excretion of urea at all visits from baseline to Day 7
- Proteinuria at baseline and at all visits from Day 1 to Day 90
- Tubular injury biomarkers, KIM-1, IL-18 and GST-alpha, in urine at baseline and at all visits from Day 1 to Day 28
- Serum creatinine at baseline and at all visits from Day 1 to Day 90
- Serum BUN at baseline and at all visits from Day 1 to Day 28.
- Systemic inflammatory serum biomarkers, e.g., IL-6, CRP, LBP, at baseline and at all visits from Day 1 to Day 28
- RRT incidence, considered as the key secondary endpoint, during the study period Day 1 to Day 28
- RRT duration, during the study period Day 1 to Day 28
- Incidence of dialysis dependency on Day 60 and Day 90
- SOFA score results at baseline, at all visits from Day 1 to Day 28 (when patient is in the ICU or intermediate care unit), and on the day of ICU or intermediate care unit discharge if discharged on a non-visit day. Note that platelets, bilirubin, creatinine and urine output are required to obtain a SOFA score.
- Quality of life, EQ-5D questionnaire at baseline, at ICU or intermediate care unit discharge, and Day 90
- Recording start and stop date, name, and mean daily dose of vasopressor and inotropic therapy for determination of shock-free days, at baseline and at all visits from Day 1 to Day 28, only required when patient is in the ICU or intermediate care unit

- Length of hospital and ICU or intermediate care unit stay by recording actual admission dates and both planned and actual discharge dates from the ICU or intermediate care unit and hospital (planned meaning when decision is taken to discharge the patient, not necessarily being the same as the actual discharge date, e.g., because of lack of beds on the regular ward)

#### **6.2.4 Safety Assessments**

The following assessments will be considered safety measurements:

- Vital signs, including blood pressure, heart rate, oxygen saturation, respiratory rate, and body temperature at baseline and at all visits from Day 1 to Day 28. During the 3 dosing days (Day 1 to Day 3), repeated vital sign measurements will be performed (see Section 6.3.4).
- Physical examination at baseline and at all visits from Day 1 to Day 28
- 12-lead ECG at baseline and at visits on Days 3 and 14
- Local laboratory at baseline and at visits on Days 1, 3, 5, 7, 14, 21, and 28:
  - Hematology
  - Clinical chemistry, including liver function parameters (aspartate aminotransferase [AST], alanine aminotransferase [ALT], gamma-glutamyl transpeptidase [GGT] lactate dehydrogenase [LDH], and bilirubin; excluding AP)
- Serology (IgG, IgE and total immunoglobulin) at baseline and at visits on Days 14 and 28
- Anti-drug antibodies at baseline and at visits on Days 14, 28, 60, and 90. Samples taken on Days 60 and 90 will only be analyzed in case of a positive result on Day 28
- Concomitant medication at screening, baseline, and all visits from Day 1 to Day 28
- AEs during the duration of the study (see Section 6.3.14)
- Mortality (monitored continuously throughout the study)

## 6.2.5 Exploratory Assessments

The following assessments will be considered as exploratory measurements:

- PK analyses performed at all visits from Day 1 to Day 7 (inclusive) in the first 120 patients from Part 1 only
- Lung function. The following must be recorded during the study:
  - Ventilation modality (e.g., non-rebreathing mask, non-invasive mechanical ventilation, invasive mechanical ventilation) and start and stop dates
  - Non-mechanical ventilation: non-rebreathing mask, or nasal oxygen delivery (liters of oxygen/min, estimated daily average)
  - Mechanical ventilation (non-invasive and invasive):
    - Arterial PaO2 (estimated daily average)
    - FiO2 and PEEP (estimated daily average)
    - Tidal volume (estimated daily average) for invasive mechanical ventilation only
    - To enable calculation of P/F ratio: PaO2 and FiO2 must be captured at the same time point. Only one simultaneous measurement will be used. In case of multiple measurements of this fraction the worst value must be used.

## 6.3 Study Procedures

The investigator or designee will determine and document in a timely manner if abnormal outcomes (e.g., abnormalities on physical examination, vital signs, or laboratory parameters) are clinically significant. Details of AE reporting are provided in Section 6.3.14.3.

### 6.3.1 Demographics and Medical History

Demographics and medical history should be recorded at baseline (see Section 13.1 [Table 13-1] and Section 13.2 [Figure 13-1]). Height will be collected at baseline for calculation of body mass index (BMI; body weight (kg) / [height (m)]).

Medical history should be recorded with special emphasis for pre-existent renal disease and the use of immunosuppressant medication, steroids, and nephrotoxic drugs. The medical

history must be documented in the patient's chart and also recorded on the appropriate page of the eCRF.

### **6.3.2 Site of Infection and Pathogen**

The location and identification of the pathogen causing the septic condition of the patient will be recorded at screening, if available (see Section 13.1 [Table 13-1] and Section 13.2 [Figure 13-1]).

### **6.3.3 Physical Examination**

A complete physical examination will be performed at baseline and at all subsequent visits up to the Day 28 visit (see Section 13.1 [Table 13-1] and Section 13.2 [Figure 13-1]). Results obtained with hand-held echography equipment may be included.

The physical examination should be performed by a physician or another study team member with appropriate training to perform the examination.

### **6.3.4 Vital Signs**

Vital signs, including temperature, heart rate, oxygen saturation, respiratory rate and blood pressure, will be measured at baseline, and at all subsequent visits from Day 1 to Day 28 (see Section 13.1 [Table 13-1] and Section 13.2 [Figure 13-1]). Vital signs in ambulant patients will be measured with the patient in a sitting position and after 5 minutes rest. Blood pressure will be monitored non-invasively. In patients who already have an arterial line placed as part of standard of care, readings from invasive blood pressure monitoring are to be recorded.

On visit days when study drug is administered (Days 1, 2 and 3), vital signs (excluding temperature) will be measured and recorded as follows:

- Immediately before the administration of the study drug
- Within 5 minutes of the start of the study drug infusion
- 30 minutes after the start of the study drug infusion
- Immediately after the completion of the administration of the study drug, which includes post-dose saline flushing
- 30 and 60 minutes after completion of study drug administration

Additionally, on Day 1 only, vital signs will be measured and recorded as follows:

- 2 hours, 3 hours, 4 hours, and 5 hours after completion of study drug administration

At all other visits, the vital signs can be assessed at any moment during the day. The time at which vital signs have been measured will be recorded in the eCRF.

### **6.3.5 Weight**

For determination of study drug dosage, body weight (in kg or lb) will be estimated or measured. The hospital admission weight (in kg or lb) will be used for study drug preparation and for calculation of fluid-corrected serum creatinine.

### **6.3.6 12-Lead Electrocardiogram**

A 12-lead ECG will be performed at baseline, Day 3, and Day 14 (see Section 13.1 [Table 13-1] and Section 13.2 [Figure 13-1]).

A 12-lead ECG with at least a 30-second rhythm strip will be recorded after the patient has rested supine or semi-recumbent for at least 5 minutes. The recording should be printed, signed, and dated by the investigator (or designee) and retained as source documentation. The ECG print should include the date and time of the assessment and the patient's study number. The interpretation of the investigator or designee will be recorded in the source documents.

### **6.3.7 Laboratory Tests Performed by the Local Laboratory**

Blood samples will be collected for local laboratory measurements at baseline, and at visits on Days 1, 3, 5, 7, 14, 21, and 28 (see Section 13.1 [Table 13-1] and Section 13.2 [Figure 13-1]). Approximately 178 to 208 mL (35 to 42 teaspoons) of blood will be collected per patient in total during the study, including tests performed in the local and in the central laboratories.

To decide when to stop RRT (see Section 6.3.9), local urine creatinine, urine volume, and serum creatinine samples will be taken and the creatinine clearance calculated. This will be based on local laboratory results.

The following laboratory tests should be performed at the visits indicated above, unless otherwise indicated:

**Clinical chemistry:** CRP, ALT, AST, GGT, urea, LDH, creatinine, bilirubin, creatine phosphokinase, total protein, albumin, glucose, sodium, potassium, chloride, bicarbonate, and lactate.

Note: AP is not allowed to be measured locally until Day 14 (see Section 6.3.8.2).

**Hematology:** hemoglobin, hematocrit, leukocytes, differential leukocytes, erythrocytes, thrombocytes, activated partial thromboplastin time.

**Pregnancy test:** only at baseline. Blood human chorionic gonadotropin (hCG) or urine hCG (dipstick). See Section 6.4 for additional details.

When the diagnosis of AKI was made according to one of the AKIN serum creatinine criteria (absolute or relative increase, see inclusion criteria 5a and 5b), the confirmative fluid-corrected serum creatinine sample with results available prior to randomization and prior to study drug administration is to confirm continuation of AKI.

Note that platelets, bilirubin, creatinine, and urine output are required to obtain a SOFA score.

### **6.3.8 Laboratory Tests Performed by Central Laboratory**

Blood and urine samples for laboratory tests at baseline and at visits from Day 1 to Day 90 as shown in Section 13.1 [Table 13-1] and Section 13.2 [Figure 13-1] will be collected and forwarded to the central laboratory for analysis. Samples will be processed, stored (if necessary), and shipped according to the instructions provided in the central laboratory manual.

Serum and urine samples for creatinine, urea, proteinuria, AP activity (baseline), sodium, tubular injury biomarkers, purines, systemic markers for inflammation, PK, serology, and anti-drug antibodies will be collected and shipped to the central laboratory.

For selected sites only, detailed instructions for iohexol and related measurements are provided in Section 13.5 (Appendix 5).

### **6.3.8.1 Endogenous Creatinine and Blood Urea Nitrogen Clearance**

The efficacy of the treatment will be investigated by calculating the time-corrected endogenous creatinine clearance. Blood urea nitrogen clearance will also be measured. To calculate the time-corrected endogenous creatinine clearance, timed urine (including measurement of volume) and blood samples need to be collected.

Urine and serum creatinine samples will be collected at all visits from baseline to Day 7 and shipped to the central laboratory. Two serum creatinine samples, one right before the start and one after the stop of the  $6 \pm 1$  hour urine collections have to be collected. Urine volume, urinary creatinine, and the average of two serum creatinine measurements will be used for the calculation of time corrected endogenous creatinine clearance at all visits from baseline to Day 7, and will be calculated by the central laboratory. The measurements from Day 1 to Day 7, inclusive, will be used to calculate endogenous creatinine clearance, the primary endpoint. Only if reliable urine collection is possible, urine will be collected on Days 14, 21, and 28 for time-corrected endogenous creatinine clearance (i.e., patient is in the ICU or intermediate care unit or hospital). If reliable urine collection is not possible, one serum creatinine sample still needs to be taken for calculating eGFR (see Section 13.1 [Table 13-1] and Section 13.2 [Figure 13-1]).

Urine must be collected daily for a period of  $6 \pm 1$  hour at baseline and from Day 1 to Day 7. The collection period will take a minimum of 5 hours, and a maximum of 7 hours. The exact duration of urine collection period and of volume collected will be recorded in the eCRF. The volume should be corrected to account for the volume of samples previously taken from the total urine initially collected.

Endogenous creatinine and BUN clearance will be calculated as follows:

$$\text{clearance} = (\text{urine volume} \times \text{concentration in urine}) / \text{concentration in serum}$$

Note: when patients during the study leave the ICU or intermediate care unit, but are still in the hospital, attempts should be made to continue with the 6-hour urine collection. If the patient is discharged from the ICU or intermediate care unit, the Foley catheter might be removed. In this case, a patient might urinate spontaneously and all efforts should be undertaken to start collecting urine produced from this time point onward. Approximately 6 hours later (exact duration needs to be recorded) the patient might urinate again and this

urine will be used for analysis, a blood sample will be drawn at this time too. The urine volume produced over the last approximately 6 hours will be entered in the eCRF. When patients are discharged from the hospital, 6-hour urine collection at home is not considered feasible or reliable and, thus, will not be performed.

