## **6.3.9 Renal Replacement Therapy**

From Day 1 to Day 7 only continuous modalities of RRT are allowed. From Day 8 onward, intermittent/non-continuous modalities such as intermittent hemodialysis are allowed.

Initiation of RRT: Initiation of RRT should be based on the criteria described by Bellomo et al (2012).

Meeting at least one criterion of the below makes the patient eligible for initiation of RRT:

1. Anuria (negligible urine output for 6 hours)
2. Severe oliguria (urine output < 200 mL over 12 hours)
3. Hyperkalemia (potassium concentrations > 6.5 mmol/L)
4. Severe metabolic acidosis (pH < 7.2 despite normal or low partial pressure of carbon dioxide in arterial blood)

5. Volume overload (especially pulmonary edema unresponsive to diuretics)
6. Pronounced azotemia (urea concentrations > 30 mmol/L or creatinine concentrations > 300  $\mu$ mol/L)
7. Clinical complications of uremia (e.g., encephalopathy, pericarditis, neuropathy)

Timing of Stopping RRT: Termination of dialysis is based on criteria as used in the VA/NIH Acute Renal Failure Trial Network Study (VA/NIH Acute Renal Failure Trial Network, 2008). If (on continuous renal replacement therapy or between intermittent hemodialysis sessions) diuresis > 30 mL/hour and there are no other indications for RRT, then endogenous creatinine clearance should be calculated using a 6-hour urine collection period. If endogenous creatinine clearance  $\geq$  20 mL/min, RRT should be discontinued. If endogenous creatinine clearance  $\leq$  12 mL/min, RRT should be continued. If endogenous creatinine clearance > 12 mL/min and < 20 mL/min, continuation or termination will be the decision of the treating physician. Exact criterion or criteria, corresponding values (e.g., sodium, potassium, or pH) and deviations (e.g., RRT not started when indicated or RRT started when not indicated) need to be meticulously recorded in the eCRF.

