## **7 Statistical and Analytical Plan**

### **7.1 Primary Endpoint**

The primary endpoint will be calculated from time-corrected endogenous creatinine clearance measurements on Day 1 (first measurement after treatment) to Day 7, inclusive. Time-corrected endogenous creatinine clearance is assessed on each day during a  $6 \pm 1$  hour period and calculated in mL/min as the mean creatinine clearance over the period, which is expected to be representative of the full 24 hours for that day. The primary endpoint is the area under the time-corrected endogenous creatinine clearance curve from Day 1 to Day 7 ( $AUC_{1-7}$ ), calculated as the average of the time-corrected endogenous creatinine clearance

values over the 7 days. Specifically, denoting  $C_i$  as the mean time-corrected endogenous creatinine clearance on Day  $i$ ,  $AUC_{1-7}$  is defined as:

$$AUC_{1-7} = \frac{1}{7} \sum_{i=1}^7 C_i$$

Any missing  $C_i$  values will be handled by linear interpolation where possible, otherwise they will be imputed by last observation carried forward (LOCF). When there are no preceding post-baseline measurements to use, the baseline measurement (i.e., prior to treatment) will be carried forward.

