8.1. Primary Efficacy Endpoint

The primary endpoint will be calculated from standardized endogenous creatinine clearance measurements on Day 1 (first measurement after treatment) to Day 7, inclusive. Standardized endogenous creatinine clearance is assessed on each day during a 6 ± 1 hour period and calculated in mL/min as the mean creatinine clearance over the period, which is expected to be representative of the full 24 hours for that day.

An adjudication committee will review the standardized endogenous creatinine clearance data on a case-by-case basis to determine the values to be used in the analysis and for the derivation of AUC_{1-7} (see [Section 8.1.2](#)). The standardized endogenous creatinine clearance (mL/min) will be calculated by PPD Biostatistics using the following formula.

$$\frac{\text{Urine Creatinine (mg/dL)}}{\text{Serum Creatinine (mg/dL)}} \times \frac{\text{Total urine volume collected (mL)}}{\text{Stop date/time} - \text{Start date/time of urine collection (min)}}$$

- The urine creatinine (mg/dL) and serum creatinine (mg/dL) assessed by the central laboratory will be used to determine the standardized endogenous creatinine clearance.
- Per protocol, two blood samples are collected to evaluate the serum creatinine, one at the beginning of the urine sample collection and the other at the end of the urine sample collection. The average of these two serum creatinine measurements will be used in the formula above to assess the standardized endogenous creatinine clearance. In case there is only one serum creatinine sample available, then the serum creatinine concentration from that one sample will be used in the formula.
- The number of minutes from the start date/time to the stop date/time of urine sample collection and the total urine volume (mL) will be derived from the Urine Volume eCRF page. If the urine volume is recorded as 0 mL, then the standardized creatinine clearance will be 0 mL/min and will not be set to missing. If the urine volume is not recorded as missing but the volume is less than 30mL/24 hrs, then the standardized creatinine clearance will be set to 1 mL/min.

The adjudicated Part 2 data will be used to determine the AUC_{1-7} (primary endpoint), while the adjudicated Part 1 data will be used in a sensitivity analysis of the primary endpoint (as described in section 8.1.4). All data will be listed.

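### The protocol's only printed formula for endogenous creatinine and BUN clearance leaves out collection time, so it gives mL per collection where mL/min is needed (minor)

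*Protocol*

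**What the plan says.** **The formula.** Protocol 6.3.8.1 states "Endogenous creatinine and BUN clearance will be calculated as follows", followed by clearance = (urine volume × urine concentration) / serum concentration. No units are given and time does not appear. On the daily urine collection, the same section says "The collection period will take a minimum of 5 hours, and a maximum of 7 hours" and "The exact duration of urine collection period and of volume collected will be recorded in the eCRF".

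**The intended unit.** Protocol 7.1 describes the daily value as "calculated in mL/min as the mean creatinine clearance over the period". SAP 8.1 multiplies the urine-to-serum creatinine ratio by volume over time, with the time defined as "The number of minutes from the start date/time to the stop date/time of urine sample collection". SAP 8.2.2.1 does the same for urea clearance.

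**The local use.** Protocol 6.3.7 says that, to decide when to stop RRT, "local urine creatinine, urine volume, and serum creatinine samples will be taken and the creatinine clearance calculated", on the basis of local laboratory results. Protocol 6.3.9 says that if diuresis exceeds 30 mL/hour and no other indication for RRT remains, "then endogenous creatinine clearance should be calculated using a 6-hour urine collection period". The result is then set against two values. At or above the upper one, "20 mL/min, RRT should be discontinued". At or below 12 mL/min RRT is to continue, and between the two the treating physician decides. Section 6.3.9 adds that these criteria are strongly preferred, that investigators may depart from them on clinical judgment with a recorded reason, and that a worksheet for these decisions will be supplied.

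**The concern.** A clearance is a flow, and the printed expression is a volume. Two patients with the same kidney function would get different results from it if one collection ran longer than the other, although the duration needed to correct this is recorded.

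For the primary analysis the SAP supplies the missing term. It does not supply it for the local calculation: SAP 8.1 specifies central-laboratory concentrations and has the biostatistics group do the computation. Protocol 6.3.7 and 6.3.9 have sites obtain a value of the same name, endogenous creatinine clearance, and compare it with figures in mL/min. The only expression the protocol prints for that quantity is the one without time, and the inputs listed in 6.3.7 do not include collection time either.

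What is at stake is consistency between sites in how that value is obtained. The timing of RRT stopping feeds two secondary endpoints, total days on RRT (compared by an exploratory ANOVA in SAP 8.2.2.1) and RRT-free days (summarized descriptively). It also determines which departures from the stopping criteria are recorded as deviations.

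**Working it through.** The plan states no figure that depends on the formula, so there is nothing to reproduce. The check is one of dimensions.

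**Inputs.** V = urine volume in mL, U and S = urine and serum concentrations in the same unit, t = collection time in minutes. Collections last 5 to 7 h, that is 300 to 420 min (protocol 6.3.8.1). The stopping check uses 6 h = 360 min, a diuresis condition of more than 30 mL/h, and the values 12 and 20 mL/min (protocol 6.3.9).

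**Formulas.**
- Protocol 6.3.8.1: V × U / S. The concentration units cancel and mL remains.
- SAP 8.1: (U / S) × V / t, in mL/min.
- Ratio of the first to the second: t.

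**Size of the mismatch.**

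| Collection | Factor t | 12 mL/min on the printed scale | 20 mL/min on the printed scale |
|---|---|---|---|
| 5 h | 300 | 3600 mL | 6000 mL |
| 6 h | 360 | 4320 mL | 7200 mL |
| 7 h | 420 | 5040 mL | 8400 mL |

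Read literally at 6 h, a printed result of 20 corresponds to 20/360 = 0.056 mL/min.

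**At the diuresis condition.** 30 mL/h × 6 h = 180 mL. To reach 20:
- with time in the formula, U/S must be 20 × 360/180 = 40;
- with the formula as printed, U/S must be 20/180 = 0.11.

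**Illustration (assumed values).** U = 60 mg/dL, S = 3 mg/dL, V = 180 mL over 6 h. Printed formula: 180 × 60/3 = 3600 mL. Time-corrected: 3600/360 = 10 mL/min. The first number is above both values in 6.3.9; the second is below both.

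**Dividing by a nominal 6 h.** This arises only if local collections also vary from 5 to 7 h and the actual time is ignored. The documents establish neither.

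| True value | Actual 5 h, divided by 360 | Actual 7 h, divided by 360 |
|---|---|---|
| 12 | 12 × 300/360 = 10.0 | 12 × 420/360 = 14.0 |
| 20 | 20 × 300/360 = 16.7 | 20 × 420/360 = 23.3 |

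Of these four readings, 16.7 and 14.0 fall in a different zone of 6.3.9 from the true value.

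**The case against.** The strongest reply is that the documents never send sites to this formula. It stands in the part of the protocol on central-laboratory tests, and its section says the central laboratory does the calculation. Sections 6.3.7 and 6.3.9 refer to each other for stopping RRT, not to 6.3.8.1. Strictly, then, the text shows that no formula is printed for the local check; that sites would use this one is an inference. This stands, and it limits the point. It does not clear 6.3.8.1, which is wrong as printed for its own purpose too.

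Second, the surrounding text makes the intention plain. Section 6.3.8.1 speaks of time-corrected clearance and timed urine and has the duration recorded; 7.1 gives mL/min, as do the values in 6.3.9. A result in the thousands set against 20 would be noticed. This also stands.

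Third, the ±1 hour window belongs to the daily efficacy collection, while 6.3.9 says 6 hours without a window. For a collection of exactly 6 hours, dividing by 360 minutes is correct. This stands, and it is why the nominal-time figures are labelled conditional.

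Fourth, the worksheet may already carry a correct formula. Its content is not in the documents, so this can be neither relied on nor ruled out.

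A reader might also infer that the primary endpoint is miscalculated, that the key secondary endpoint is biased, or that every patient checked would be read as above 20 mL/min. The documents support none of these. SAP 8.1 divides by minutes, RRT incidence depends on starting RRT and not on stopping it, and the third reading needs a literal use of the formula that the stated units make implausible. Nor are sites bound to act on the result, since departures are allowed with a recorded reason.

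**Conclusion.** The omission is real. Protocol 6.3.8.1 sets out a calculation that, followed as written, gives mL per collection, and it disagrees with protocol 7.1, protocol 6.3.9 and the SAP formulas by a factor equal to the collection time in minutes (360 at 6 h).

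The consequence is small. The primary endpoint and urea clearance are protected by the SAP, and RRT incidence is untouched. The exposure is the local calculation used when considering stopping RRT. There the realistic risk is that sites repair the formula in different ways; a 360-fold error is unlikely to go unnoticed. The nominal-time misreadings (a true 20 read as 16.7 or 23.3) rest on two assumptions, a 5-to-7-hour spread in local collections and disregard of the actual time. Severity: minor.

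**What to change.** In protocol 6.3.8.1, add the actual collection time in minutes to the denominator and state the unit mL/min, matching SAP 8.1 for creatinine and SAP 8.2.2.1 for urea. Reconcile 6.3.7, 6.3.8.1 and 6.3.9 so that it is clear which calculation, in mL/min, the local check refers to.

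This does not require the SAP's averaging of two serum samples for the local check. No view is taken on the 12 and 20 mL/min values, on serum sampling for the local check, or on any stopping rule.

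The cost is a one-line correction with a cross-reference and a short note to sites. The RRT worksheet should be checked for consistency and changed only if it prints a formula that disagrees.
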